7 GENERAL STATISTICAL CONSIDERATIONS

7.1 ANALYSIS SETS

The following analysis sets are planned for the study and will apply to the endpoints through the end of Phase 2. There are no prespecified analysis sets for Phase 3; all available data will be used to summarize Phase 3 endpoints.

7.1.1 ITT (Intention to Treat) Analysis Set

The ITT analysis set includes all subjects that are enrolled in the study. All safety analyses (other than primary analysis for primary safety endpoints) will be based on the ITT analysis set.

7.1.2 mITT (modified Intention to Treat) Analysis Set

The mITT analysis set is a subset of the ITT analysis set. The mITT analysis set will consist of subjects who have entered the hybrid closed-loop phase of the study successfully. The mITT analysis set will be used as the primary analysis set for all primary and secondary endpoints (both safety and effectiveness), and other clinical outcome data.

7.1.3 PP (Per Protocol) Analysis Set

The Per-Protocol (PP) analysis set is a subset of the mITT analysis set. Subjects will be included in the PP analysis set if they have a minimum of 80% system use during Phase 2 inclusive of manual and hybrid closed-loop (automated) modes over a minimum duration of 10 weeks and have completed the study without major protocol deviations. The PP analysis set will be used as supportive analysis for the endpoints. The following will be considered major protocol deviations:

- Major inclusion/exclusion criteria deviation
- Significant protocol non-compliance that may confound the study objective data (e.g., use of prohibited medications)

The list of subjects excluded from the PP analysis set will be determined prior to analysis of Phase 2 endpoints. If the PP analysis set does not differ from the mITT analysis set, separate analyses will not be presented.

Statistical Analysis Plan

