## PROTOCOL SUMMARY

Protocol title	Evaluating the safety and effectiveness of the Omnipod Horizon™ Automated Glucose Control System in patients with type 1 diabetes
Protocol ID	G190270
Purpose	To evaluate the safety and effectiveness of the Omnipod Horizon™ Automated Glucose Control System in patients with type 1 diabetes.
Design	This study is a single-arm, multi-center, prospective clinical study
Enrollment	
A total of up to 240 subjects will be enrolled in the study in order to obtain a minimum of 200 evaluable subjects.
 
The study will consist of three phases:
 
 
1) 14-day standard therapy outpatient phase (Phase 1)
 
2) 13-week outpatient hybrid closed-loop phase (Phase 2) 
 
• Phase 2 excludes periods due to a study pause
 
 
 
3) 12-month hybrid-closed-loop extension phase (Phase 3)
 
 
Subjects will be enrolled across 12-20 clinical study sites. The 200 evaluable subjects will be comprised of two age cohorts of 100 subjects each as follows:
 
 
• 100 subjects aged 6-13.9 years
 
• 100 subjects aged 14-70 years
 

Indication	
The Omnipod Horizon™ Automated Glucose Control System is a single hormone insulin delivery system intended for the management of diabetes in persons requiring insulin. Continuous subcutaneous insulin infusion may be delivered by user-defined settings (manual mode) or automatically adjusted in response to feedback from a continuous glucose monitor (CGM).
 
The Omnipod Horizon™ System can automatically increase insulin delivery based on CGM sensor glucose values and can decrease or suspend delivery of insulin when the glucose value falls below or is predicted to fall below predefined threshold values. The Omnipod HORIZON™ System is interoperable with compatible iCGMs and ACE pumps.
 
The Omnipod Horizon™ System is designed to assist patients with diabetes in achieving glycemic targets set by their health care providers.

Study duration	The study is expected to be completed within 30-months which includes clinical site initiation to completion of Phase 3 and all data entry and monitoring procedures. The sponsor intends to submit results from Phase 2 for marketing clearance after data collection for Phase 2 is complete. The results from Phase 3 will be submitted separately.

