## 9.9 Visit 13 (End of Phase 2)

**Visit 13** will be conducted either over the telephone or in person at the clinical study site on Study Day  $94 \pm 3$  days. This visit will include:

- A1C (blood draw sent to NGSP laboratory)
- Pregnancy test for women of childbearing potential (if visit is conducted in person at the clinical site)
- Review of concomitant medications
- Height (if visit is conducted in person at the clinical site)
- Weight (if visit is conducted in person at the clinical site)
- Assessment of vital signs (if visit is conducted in person at the clinical site)
- Assessment of AEs since last visit
- Completion of questionnaires (See Table 4: Questionnaires for specific requirements by age group):
  - WHO-5
  - EQ-5D
  - T1DDS
  - DTSQc
  - Hypoglycemia Confidence Scale
  - HABS
  - PSQI
  - IDSS (T1)
  - SUS
  - PAID-(Teen, Child)
  - INSPIRE-(Adult, Youth, Parent)
    - Used to measure a caregiver's experience of the support they receive
  - Human Factors (HF) Questionnaire
    - Measures trust in the Horizon System

- Clarke Questionnaire
- Discontinuation of Horizon Data Portal monitoring if not continuing into Phase 3
- Return study devices if not continuing into Phase 3 (Omnipod Horizon™ System, CGM, BG and ketone meters)
- Complaints/device deficiencies such as occlusion alarms and system hazard alarms since last visit
- Device uploads for BG and ketone meter
- Data review of Automated Mode use by clinician

This visit will mark the discontinuation of Phase 2 and mark the end of the study for subjects not continuing to Phase 3.

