2.3 STUDY SCHEDULE

The study will consist of a 14-day outpatient standard therapy (ST) outpatient phase (Phase 1), a 13-week outpatient hybrid closed-loop (HCL) phase (Phase 2), and a 6-month hybrid closed-loop extension phase (Phase 3). The sponsor intends to submit results from Phase 2 for marketing clearance after data collection for Phase 2 is complete.

A subset of subjects will participate in supervised challenges during any consecutive 5-day period during the 13-week HCL Phase 2:

- A minimum of 100 subjects 6-13.9 years

Statistical Analysis Plan

- A minimum of 60 subjects 14-70 years

Subjects having completed the prepivotal study may participate in this pivotal study and begin at Visit 5 during Phase 2 (HCL phase) since Phase 1 (ST) was completed as part of the prepivotal study and is not required to be repeated. Prepivotal subjects do not require rescreening if their original screening is within 45-days prior to Visit 5.

The Horizon™ System has two modes. In Manual Mode, the system will function equivalently to the Omnipod DASH System. This includes delivering insulin at programmed basal rates and bolus amounts with the option to set temporary basal profiles. In Automated Mode, the system will support the use of multiple target glucose values. The programmed basal rates, glucose targets and bolus calculator settings will inform the MPC (model predictive control) algorithm for insulin dosing parameters.

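### The per-protocol set requires completion of the study, but its membership is fixed before the Phase 2 analysis, when many or most extension subjects will not have finished

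*SAP*

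**What the plan says.** SAP 7.1.3 builds the PP set from the mITT set by three conditions joined by *and*: at least 80% system use during Phase 2 (manual and automated modes together), a 10-week minimum, and completion. The last two read "over a minimum duration of 10 weeks and have completed the study without major protocol deviations". The same section fixes the timing: "The list of subjects excluded from the PP analysis set will be determined prior to analysis of Phase 2 endpoints". Protocol 13.4.3 carries the same completion condition. Its list is also settled before analysis, though it does not name Phase 2 at that point.

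Four other places bear on the meaning:

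- SAP 7.1 says that the analysis sets "will apply to the endpoints through the end of Phase 2" and that Phase 3 has none.
- SAP 2.3 states: "The sponsor intends to submit results from Phase 2 for marketing clearance after data collection for Phase 2 is complete". The Protocol Summary adds: "The results from Phase 3 will be submitted separately".
- Protocol 9.9 says that Visit 13 will "mark the end of the study for subjects not continuing to Phase 3". Protocol 10.9 labels Visit 23 the end of study.
- SAP 6.6 takes end-of-Phase-3 data from Visit 19, and SAP 2.3 gives Phase 3 a length of 6 months. The protocol gives 12 months.

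**The concern.** Membership has to be decided at a time when one of its conditions cannot be met by subjects still in the extension. A subject who declined Phase 3 has completed the study at Visit 13. A subject who went on, with equally good adherence and no deviations, has not. Applied as written, the rule sorts subjects by their decision about the extension, which is not a measure of adherence in Phase 2.

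That decision may be related to how the subject fared on the device, so the PP set could differ from the mITT set for reasons unrelated to protocol compliance. The documents do not allow the direction of any such difference to be judged. PP is the set named as supportive for both primary endpoints (SAP 4.2) and for both secondary endpoints with hypotheses (SAP 6.5). A disagreement between PP and mITT results would then be hard to interpret.

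**Working it through.** **The plan's own figures.** Neither document states an expected PP size. The nearest figures are the 35 (A1C) and 31 (time in range) evaluable subjects in SAP 4.1. They reproduce as the smallest n for which a paired t-test at one-sided 1.25% has 90% power, using the noncentral t with noncentrality (difference/SD) × √n:

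- A1C: 0.5/0.8 gives n = 35, power 0.906.
- Time in range: 10/15 gives n = 31, power 0.905.

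This point does not affect them.

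**Inputs for the timing check.** Visit 13 is Day 94 ± 3 (protocol Table 2). Visit 19 is Day 270 ± 5 and Visit 23 is Day 450 ± 5 (protocol Table 3).

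**Time from the end of Phase 2 to the end of study, continuing subjects**

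- SAP end of Phase 3 (Visit 19): 270 − 94 = 176 days. Shortest within windows: (270 − 5) − (94 + 3) = 168.
- Protocol end of study (Visit 23): 450 − 94 = 356 days. Shortest within windows: (450 − 5) − (94 + 3) = 348.

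**How many continuing subjects could have finished when the list is fixed?** The documents give no accrual dates, so this needs assumptions. Suppose Phase 2 end dates are spread evenly over W days and the list is fixed when the last subject reaches Visit 13. Then:

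share finished = max(0, (W − gap)/W)

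| Assumed W (days) | 6-month Phase 3 (gap 176) | 12-month Phase 3 (gap 356) |
|---|---|---|
| 60 to 120 | 0% | 0% |
| 180 | 4/180 = 2% | 0% |
| 240 | 64/240 = 27% | 0% |
| 365 | 189/365 = 52% | 9/365 = 2.5% |
| 433 | 257/433 = 59% | 77/433 = 18% |

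The last row is the widest spread that fits the protocol's 30-month study duration: about 913 days, less 450 of participation and 30 of screening, leaves 433. A delay between the last Visit 13 and the fixing of the list would raise every share.

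The spread could go either way. SAP 2.8 says that most subjects have Phase 2 data from both before and after a pause, which would tend to bunch the end dates. Protocol 9.11 lets up to 42 subjects defer recommencement, which would widen them.

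**After the change.** If the condition refers to Phase 2, every subject can be classified at Visit 13, before the Phase 2 analysis, whatever W is.

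**The case against.** The strongest reply is that context settles the meaning. The sets apply only through the end of Phase 2, system use is counted in Phase 2, and the list is fixed for the Phase 2 analysis. A reading that strips the set at the moment it is needed is not one that the SAP could operate. This mostly stands: completion of Phase 2 was very probably intended. It does not remove the defect. SAP 7.1.3 names Phase 2 for system use and for list timing but the study for completion, the protocol attaches end of study to Visit 23 for continuing subjects, and neither document defines completion as Visit 13.

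A second reply is that little hangs on it. This stands in full. The mITT set carries the primary and secondary analyses, study success rests on safety rates (SAP 2.5), and the primary effectiveness endpoints are not to support labeling claims (SAP 4.2).

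Three stronger readings are tempting, and the documents do not support them:

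- *The 10-week minimum contradicts the completion clause.* It does not. The conditions are joined by *and*, so a subject who leaves at week 11 fails one and is out. At most the conditions overlap. The 10-week rule can still do work, because it attaches to system use: protocol 12.3.2 foresees temporary discontinuation of the device, and protocol 13.4.3 does not count Manual Mode use during a pause.
- *Dropout in Phase 3 would remove subjects from a Phase 2 analysis.* That requires the list to wait for the end of the study, which SAP 7.1.3 rules out. The documents also give no Phase 3 dropout rate from which to size it.
- *The membership rule could be chosen after results are known.* SAP 7.1.3 settles the list before the Phase 2 endpoints are analysed.

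**Conclusion.** The conflict is real on the wording and small in consequence. Read literally, the Phase 2 PP set would hold subjects who declined the extension plus any continuing subjects who had already finished.

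A reader might infer that it would hold almost no continuing subjects. The table supports that only for spreads up to about 180 days with the SAP's 6-month Phase 3, or about 365 days with the protocol's 12-month Phase 3. With a wide spread and the 6-month version, half or more of the continuing subjects could have finished. The number who decline the extension is not given either, so the size of the PP set cannot be stated. These shares rest on the assumed even spread of Phase 2 end dates and on fixing the list at the last Visit 13.

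No primary or tested secondary conclusion changes, because both rest on the mITT set. This is a clarification worth making, not a flaw in the main analysis.

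**What to change.** In SAP 7.1.3 and protocol 13.4.3, replace the completion clause with: *have completed Phase 2 (through Visit 13) without major protocol deviations during Phase 1 or Phase 2*. Leave the 80% use and 10-week conditions unchanged. The completion requirement should stay: dropping it would admit subjects who left Phase 2 after week 10 and so define a different population, which this problem does not call for.

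The cost is one sentence in each document, made before the exclusion list is fixed. Sample size, alpha and data collection do not change. The length of Phase 3 (6 months ending at Visit 19, or 12 months ending at Visit 23) should also be reconciled between the documents, but after this change PP membership no longer depends on it.

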7.2 CONTROL OF SYSTEMATIC BIAS

Several measures are incorporated into the study design to help minimize study bias as follows:

- 1) This is a multi-center trial to help ensure that investigator or site or subject enrollment bias is minimized. Selection of subjects will be made from the Investigator's usual subject load. Consecutively eligible subjects should be enrolled into the study.
- 2) This document specifies appropriate statistical methodology to ensure that bias is minimized.
- 3) The effectiveness measures will be based on the direct output from the device or are analyzed at a NGSP certified central laboratory, ensuring objective reporting.
- 4) An independent Medical Monitor will adjudicate all SAEs and device-related adverse events; the Medical Monitor's assessment of adverse events will be used for regulatory reports, product labeling, and publications or presentation.

7.3 POOLING DATA ACROSS CENTERS

Up to 20 clinical sites will enroll subjects into the study. No single site should enroll more than 24 subjects for each age cohort. For the purposes of statistical analyses of primary effectiveness endpoints, data from all study centers will be pooled. The primary effectiveness endpoints will also be presented by center. The appropriateness of pooling subjects across sites will be assessed graphically or utilizing an appropriate statistical test.

7.4 CALCULATION OF PERCENTAGE OF TIME IN RANGE

Several effectiveness endpoints involve calculation of percentage of time in a specific glycemic range. These endpoints will be based on the direct output from a device (either a CGM or The Omnipod Horizon™ Automated Glucose Control System). The percentage of time in range (TIR) will be calculated as:

$$100 \times \frac{\text{\# of CGM readings in range}}{\text{\# of evaluable CGM readings}} = \text{TIR\%}$$

The following CGM readings will be excluded from analysis, and therefore, from calculation of TIR endpoints:

- No glucose value is provided in the device output, such as due to an error or device deficiency during which the device does not record glucose readings
- CGM readings reported prior to start of standard therapy phase or after subject's discontinuation from HCL

Statistical Analysis Plan

